#### Minimal Risk; Possible discomfort when responding to questions

The risks of participating in SAGE LEAF are minimal. In past research, we have not observed any participants experiencing serious or lasting distress in response to similar interventions or assessments. The intervention has been user-tested to remove any material/content that might be upsetting or insensitive, to reduce the chances of using those questions in future versions. Therefore, risk of discomfort is extremely low. However, some might experience slight discomfort when asked about their emotions, coping, anxiety, and stressful events, or reflecting upon experienced negative emotions. Participants are notified that they may skip any questions they do not wish to answer.

SAGE LEAF study staff who are interacting with participants or monitoring their responses to study procedures will be alert to indicators of elevated distress or possible suicidality. If a SAGE LEAF study staff member observes a possible sign of significant distress and/or suicidal ideation, they will follow an established safety protocol (attached), working together with designated team members to evaluate the severity of the situation, generate a tailored response, and complete final responding and reporting.

#### "Pollyanna"

The risk of proclaiming the importance of positive affect in the stress and coping process is that it may appear to minimize the pain and serious individual and societal consequences associated with major stressful events. We are not advocating a simplistic "don't worry-be happy" approach, nor do we believe that simply increasing positive emotion will prove to be a cure-all for the very real and complex issues facing caregivers. Such a Pollyanna-ish stance could easily degenerate into blaming the caregiver for not thinking the positive thoughts that may prevent depression or other negative consequence of enduring stress. However, we argue that an intervention to increase positive emotions sets the stage for adaptive coping. Ultimately, given the high levels of caregiver burden, depression, and anxiety documented in AD caregivers, we consider increasing positive emotion to be an inherently worthwhile intervention goal.

While our study focuses on positive emotion, we emphasize that SAGE LEAF is not a replacement for therapy, nor is it considered a treatment for depression or anxiety. Participants are encouraged to follow the guidelines of their health care provider and advised that they should not put off starting therapy and/or medication or stop treatments recommended by their health care provider.

#### Withdrawal of participants

If a participant wishes to withdraw, he/she can communicate this on the phone or via email to the project director. Study staff will also be monitoring communications and potentially withdrawal requests coming through on the study website or study email. The participant will then be promptly withdrawn from the study, their data collected and eventually analyzed only up until the point of withdrawal. No further data will be collected after a participant has been withdrawn. We will document the reason for withdrawing.

## **18.0** Provisions to Protect Participant Privacy and Data Confidentiality:

#### Confidentiality in data

The risk of loss of confidentiality is extremely low. Identifiable information will be collected using REDCap which uses industry-standard encryption to protect participants' information while in transit from the moment data is entered to the moment it is stored on HIPAA compliant servers. Data is never fed back to participants or displayed on the participant website. Access to REDCap is granted to key personnel and all study staff

handling personally identifiable information will have taken the CITI Human Subjects Training Course. Participants will be assigned and identified by a unique Study ID on the SAGE LEAF platform, and their information will be stored in encrypted form on Northwestern computers. Any hard-copy documents will be stored in locked cabinets in the Department of Medical Social Sciences and all electronic copies of data, study emails, or records will have double-protection through password-protected access for NU servers and to REDCap. Even if a participant's account is later compromised, submitted information on the website is protected and not released.

The REDCap instance at Northwestern supports the SMS text messages. We are using REDCap's feature to integrate SMS text messaging with Twilio to send the assessments. Access to the phone numbers are password-protected and secure. The same data protections that exist for the REDCap PHI exists for the SMS messaging feature as well. Assessment data will not be stored locally on the phone or any device. If receiving an assessment via text, the message will include a link to a web-based survey (protected and hosted by NUCATS). If issues arise with the SMS feature, we will immediately contact the REDCap administrators at Northwestern University to resolve any issues.

The SAGE LEAF online platform is hosted by Bright Outcome and is protected by end-toend encryption and password measures. Participants will be able to access the SAGE LEAF intervention on their computer, tablet or mobile phones with an internet connection. Participants will submit their home practice through the website (i.e. gratitude journal) and submit their feedback for the lessons, since participants are encouraged to visit the site every day. IRB-approved NU study staff will be able to access the data collected through the platform through direct export. No data will be stored locally on participants' devices.

#### Confidentiality in general

Once a participant is enrolled in the study, there is the chance someone might see a participant filling out assessments or reading the positive emotion skills on the platform. To protect participant privacy, we encourage all participants to find a private room with a closed door and to use headphones (if needed) when completing online modules or participating in the feedback interview. We will also encourage participants to be mindful and aware of their location (i.e., in a public or crowded space) when filling out their online assessments. Since the assessments are completed online, this allows for flexibility and participants can answer the questions from the comfort and privacy of their own home on their mobile device/tablet computer/laptop etc.

## **19.0** Data Monitoring Plan to Ensure the Safety of Participants:

We have developed the following data and safety monitoring plan. Our goal is to collect data on acceptability, adherence, and retention of the intervention through self-report

measures and by tracking website usage and engagement. We aim to do so in a way that protects and ensures participants safety and confidentiality.

The assessments and intervention sessions pose no more than minimal risk to participants. The data and safety-monitoring plan identifies the PI as the primary monitor of risks to human subjects in the form of data and safety related risks. The study's biostatistician is the back-up data custodian to the PI, advising and providing support in data decisions. Any serious adverse events will be promptly reported to the institution's IRB and project officer of the funding source by the study PI. Risks, monitoring procedures, and reporting and action plans are described below for both data and safety related risks.

#### Data Risks and Monitoring

Data related risks. Data related risks to participants could consist of circumstances where an insufficient amount of data was collected to answer the research questions, or a breach of confidentiality where the safety of identifiable data has been compromised.

Data monitoring procedures. The PI, [name] will be the primary data custodian for SAGE LEAF. Overall recruitment goals, missing data, and follow-up failures will be monitored by the project manager, and the PI will receive regular updates and maintain constant communication with the project manager, and the rest of the team; at first bi-weekly, then monthly as needed. The biostatistician will also provide ongoing monitoring of study progress and advise with proposed changes and precautions, if necessary (i.e. updates to protocol to meet recruitment goals, etc.). Post-doctoral fellows and co-Investigators who will be assisting with data analysis will be added to the IRB.

Data risk reporting and action plan. The project manager will oversee the data safety and monitoring plan, data management, and data security. She will work alongside the PI and the Project Director to compile the recruitment numbers during all phases of the study and responsible for assuring completion of required assessments, maintaining databases, and identifying missing data and missing follow-up assessments.

#### Safety Risks and Monitoring

Safety related risks. Safety related risks could consist of:

- 1) Emotional discomfort while using the SAGE LEAF platform
- 2) Emotional discomfort while completing assessments
- 3) Loss of confidentiality in data
- 4) Loss of confidentiality in general
- 5) "Pollyanna" effect and mistaking the intervention as therapy
- 6) Signs of distress or revealing identifying information on the "Discussion" forum

Safety monitoring procedures. All safety related risks will be monitored routinely throughout the study. (1-2) It will be made clear to participants that they are allowed to skip any exercises or questions that may cause them emotional distress. Participants are provided instructions on how to use the website, log-in, access the course, and are given the contact information of the Project Director, PI, and the designated study email. Guidelines and videos to use the website are provided. Participants can email or call study staff and the study is generally staffed Monday-Friday 9am-5pm except holidays, etc.

[name] is on the SAGE LEAF study team and she is a clinical psychologist. She is also a Research Professor in the Department of Medical Social Sciences, Feinberg School of Medicine. She will be the main point of contact and the study advisor for questions regarding safety concerns. She will help the team make recommendations and take research precautions to ensure the safety of our participants.

Study staff are monitoring the website weekly and will be trained to respond immediately to participant needs and/or questions on technology and the platform. There is also a FAQ page on the website for frequently asked questions. If a question is not listed/answered on the FAQ page, participants may call or email study staff. Based on our experience conducting prior trials of online self-guided delivery of positive affect skills (e.g. MARIGOLD, LARKSPUR), the study team is well versed in handling/managing instances that might require providing caregivers with additional resources. The PD will be the main point of contact and the study advisor for questions regarding safety concerns. She will help the team make recommendations and take research precautions to ensure the safety of our participants.

(3) The security of confidential information will be monitored regularly. Participants will be informed that their responses will be kept confidential and not used against them in any legal, online modules in a private space and to be mindful of where they complete their online assessments, so as to limit the chance of someone overseeing their answers and to limit exposures of their responses from their computer/tablet/phone screen.

(5-6) In the event that a participant contacts the study directly to report severe distress or suicidality, or reveals this information online in an email or via the website's "Discussion" feature, the project manager or study team member will immediately alert the PI. The PI will review the situation and take immediate, appropriate steps. If the situation is serious, designated research staff will promptly respond to a distressed participant with appropriate information about how to seek help. In previous studies, we have developed monitoring plans for responding to signs of distress in an online forum. Study staff have the ability to archive/delete messages that are inappropriate to keep the discussion board related to discussing topics on SAGE LEAF. Based on our past experience conducting online studies with a discussion feature (e.g. MARIGOLD, LARKSPUR), the risk of these occurrences is minimal and the study team is well versed in handling/managing these instances, if they happen. Safety risk reporting and action plan. Any participant in need of treatment due to distress will be referred for appropriate services by the project manager. In severe cases, the PI will be informed immediately. The project director will report breach of confidentiality risks incurred by participants to the PI. The PI will be responsible for informing the IRBs and the Project Officer immediately of any life threatening incidents (although this risk is very low and not expected to happen). The PI will take appropriate action to stop the study, release a participant from the study, or modify procedures to reduce and/or eliminate the occurrence of the abovementioned risks occurring at an unacceptable level.

Adverse events. Due to the nature and scope of this study, we do not anticipate any adverse events. However, in the case that an adverse event arises, it will be tracked and the PI informed within 24 hours to assess the situation and follow-up. An adverse event form will be developed detailing the problem, actions taken, supervisor notes, and follow-up steps performed. The form will be immediately sent to appropriate agencies, including the IRB and NIH. Any action recommended by one of the IRBs will be conveyed to the NIH. The PI will be responsible for the monitoring and reporting of any adverse events. The co-investigators will be consulted as appropriate.

All problems having to do with subject safety will be reported by the Principal Investigator to the IRB within ten working days. Specifically, the following will be reported, in writing: 1) all serious adverse events associated with the study procedures, and/or 2) any incidents or problems involving the conduct of the study or participation, including problems with the recruitment and/or consent processes. The Principal Investigator will provide a discussion of any problems noticed during each year in the course of the study to the IRB and NIH on an annual basis.

If, during the course of communicating with study staff (e.g., synchronously on phone or asynchronously via email), a participant indicates severe elevation of distress or possible suicidal ideation, study staff will follow the attached Safety Protocol, which has been developed based on procedures used in their prior studies of positive emotion skills delivered online. Staff who are responsible for communicating directly with participants will be trained on the Safety Protocol by [name] and/or the PD. Trainees will be responsible for reading the entire Safety Protocol prior to training. Then training will include: a discussion/review of all elements of the Safety Protocol; time for all trainees to discuss any relevant experience and ask questions; and the opportunity to role play using the telephone template responses.

## 20.0 Long-term Data and Specimen Storage and Sharing:

[name], PI, is involved in the development of the online intervention, analysis, data interpretation and manuscript write-up. She will have secure access to the data housed at NU. No other Northwestern personnel will have access to the data unless he/she is listed on the IRB as study personnel. [name] and her NU collaborators will also use

statistical programming on FSM desktops/computers and store analysis documents on FSM servers.

Data, manuscript drafts, forms and other study-related documents will be stored on secure FSM servers through the Department of Medical Social Sciences (MSS). For the information that must be identifiable for the purposes of the study (i.e. name, phone number, email address for facilitator/participant contact), this information will have added layers of protection (via password access to the file). Participants will be coded and identified by a unique participant ID.

Data input, processing, tracking and storage will happen at Northwestern University. [name] has oversight over each part of the process. Path to storage: Bright Outcome platform REDCap platform  $\rightarrow$  Northwestern HIPAA-compliant server (storage and analysis) on the FSMFILES MSS Departmental Server.

Identifiable data will only be shared internally amongst researchers listed on the IRB. Only IRB-approved individuals will have access to data through encrypted networks like the FSMFILES network or have permission to download datasets directly from REDCap (i.e. the PI, the biostatistician, the project director, IRB-approved study staff). De-identified data might be shared with collaborators for the purposes of data analysis, secondary data analysis, manuscript-writing, using Northwestern Box. We will take precautionary measures to protect the confidentiality of our participants.

## 21.0 Qualifications of Research Team to Conduct the Research:

Northwestern University (NU), whose component schools and clinical affiliates form the foundation of this proposal, supports and promotes a vibrant and ever-growing community of clinical and translational scientists that is passionately committed to improving human health. Northwestern is one of the premier undergraduate and graduate universities in the world. It is ranked 12th among US national universities by US *News & World Report*, and is ranked in the top 30 world-wide. NU has notable strengths in medicine, public health, chemistry, nanotechnology, life sciences, engineering, communications, law and business/management. Northwestern's sponsored research awards grew to \$620 million in fiscal year 2015, the largest amount in the University's history and a 4 percent increase over 2014's \$593.9 million. NU is located in Evanston and Chicago, Illinois. The University has a long history of leadership in interdisciplinary research programs and centers. More than 90 school-based centers and 26 University centers support interdisciplinary research that spans a wide spectrum of areas. Investigators with a Northwestern affiliation have access to the Galter Health Sciences Library at Northwestern University's Feinberg School of Medicine and all other Northwestern University libraries, including the Pritzker Research Library at Children's Memorial Hospital.

The proposed project will be based in FSM's **Department of Medical Social Sciences** (MSS). MSS was established in 2009, with [name] as founding and current chair, and provides a unique scientific home for applied researchers, integrating biomedical and social science approaches to improvement of health and health care delivery in diverse populations across the lifespan. Research themes include health measurement, quality of life measures, developmental mechanisms of health and disease and statistical tools to support clinical research with strength in application to specific disease processes such as cancer, neurologic disease, and early onset psychopathology. MSS is a catalyst for scientific integration across biomedical and social / life sciences campuses. MSS research cuts across traditional disciplinary boundaries, with collaborative ties with a broad range of research institutes and clinical departments across the University.

Within MSS, there is adequate office space and computer work stations for all planned staff and secure data storage (paper and electronic) designated for the proposed study. MSS has its own internal Information Technology group that manages all hardware, software, and support needs for the department. Department computers are generally on a three year replacement cycle and use whatever technology is current at the time of replacement. The computers use either Windows or MacOS operating systems and run individual firewalls, antivirus, backups, and disk encryption that are centrally managed. Servers, while managed by the department IT group, are hosted at the University Data Centers that are shared by all departments. Servers provide web services, database services, file storage, and print services. These are secured behind Data Center firewalls with specific ports open for each specific service. Network access is limited to authorized University IDs. Physical access is limited to specific IT personnel using three factor authentication including biometrics. Files are backed up daily and databases are backed up every two hours. The department currently utilizes 24 servers in a combination of physical machine and virtual machine configurations. Protected health information and personally identifiable information that are stored on MSS database servers and on MSS file servers are layered with various physical and electronic access protections and policies to ensure HIPAA compliance. There are approximately 120 laptop and desktop computers utilized by department faculty and staff for day to day computing needs, along with over 50 laptops dedicated to specific studies.

In addition, we will be working with **Bright Outcome**, a healthcare technology company that has built successful collaborations with other investigators at MSS. They have worked with other clients such as the Centers for Disease Control and Prevention, the National Institute of Mental Health, the National Institute of Nursing Research, and the National Cancer Institute.

## 22.0 Statistical Analysis:

Statistical Analyses

We will calculate the medians and interquartile range (IQR) for primary measures that assessed the (1) usability, (2) usefulness, (3) feasibility, and (4) acceptability of the SAGE LEAF platform. In addition, we will calculate supplementary user metrics based on data collected by the platform (e.g., percentage of home practice activities completed and percentage of videos watched) that reflect various aspects of engagement. We calculated the means and SDs for the Social Presence Scale and applied them as a correlate with measures of usability, usefulness, feasibility, and acceptability. For measures related to preliminary outcomes, we will perform paired, 1-tailed t tests on the data collected during the baseline and postintervention assessments to examine changes in means. Analyses will be conducted using Excel (Microsoft Corporation) and R Studio (Posit).

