One such format that has been widely adopted is the *self-guided* online intervention, where participants have access to the content on their own with minimal guidance provided. Previously, we utilized this medium to deliver a positive emotion intervention for individuals with elevated depression symptomatology. But while such interventions reduce barriers for participation, they are beset by high rates of attrition and poor adherence. Parallel research on other self-guided resources, namely Massive Open Online Courses (MOOCs), have found that the construct of *social presence* – or the ability to perceive others in an online environment – can enhance retention and engagement. Social presence may include features like providing welcome messages, displaying participant profiles, and facilitating online discussion amongst participants. Hence, eHealth and mHealth interventions are likely to benefit from the application of these social features.

With these considerations in mind, such social features may be particularly beneficial for caregiver participants; who experience higher levels of social isolation and loneliness compared to their peers. Hence, the objective of this proposal is to adapt the existing positive emotion intervention for SAGE LEAF – a socially enhanced, online intervention for Alzheimer's caregivers. If successful, SAGE LEAF may be scaled as an online resource that caregivers could utilize to better cope with the stressors of caregiving.

For the **1**) **user test**, we will be evaluating the SAGE LEAF platform's usability and usefulness. Non-Alzheimer's dementia caregivers recruited from the Northwestern Cognitive Neurology and Alzheimer's Disease Center (CNADC) (N=20) will participate in an extended user test where they will receive full access to the SAGE LEAF intervention, and provide their feedback through surveys and interviews on the platform's usability and usefulness upon conclusion of the 6-week program. Subsequently, the necessary refinements to the platform will be made based on the feedback received.

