Next, we will conduct a (N=30) single-arm pre-post 2) **pilot test / feasibility study** of SAGE LEAF for AD caregivers. Participants will receive access to the SAGE LEAF platform and complete the positive emotion skills intervention over 6 weeks. We will evaluate the number and percentage of participants retained at the post assessment as well as the means and ranges for the proportion of intervention content completed (i.e., number of pages viewed out of the total possible pages across all skills and lessons in the intervention) and participants' acceptability ratings (i.e., participants' ratings of whether they would recommend SAGE LEAF to other AD caregivers).

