#### 6 Sessions over 8 weeks: approx. 30 minutes/online module Week Self-Guided Intervention "Online Lessons"

The SAGE LEAF online lessons consist of 6 modules for the intervention; one module unlocked per week over 6 weeks, but participants will have an 8-week period to complete the 6-module intervention. The intervention content, emotion reporting forms, and assessment questionnaires are all mobile-enabled and, thus, can be completed on desktop, laptop, tablet, or smartphone. In this self-guided intervention, skills will be delivered within 8 weeks. Participants will also have access to social features, which include the discussion board, didactic videos from study staff, virtual awards, etc.

Participants can participate from their home computer, smartphone, or a tablet from a location with wifi. A week will consist of 1-2 days of didactic material and 5-6 days of reallife skills practice and reporting. Participants cannot skip ahead, and can only progress to the next lesson if they have completed the current one, but they can return to old lessons or exercises if they wish to. Participants will receive email or text notifications throughout the study, and will have access to a control panel to configure their preferences. As part of the daily home practice, intervention participants will be asked to complete the daily stress and emotion questions. Other data collected from the Bright Outcome platform will be securely stored on Northwestern servers, accessible only to IRB-approved study staff. These data include number of log-ins, completed home exercises, number of skills completed, data from the daily emotion reporting surveys, number of awards earned, discussion posts, etc.

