#### Measures

Participants will complete self-report questionnaires at 2 time points over approximately 8 weeks. The assessments will be named by their time point "T", e.g. T1 (baseline) and T2 (approx. 6-8 weeks from baseline). At T3 (8 weeks from baseline), participants will participate in a 45-60 min feedback interview (see attached interview guide) through videoconferencing with a member of the study team. All self-report assessments will be completed from home via tablet, a home computer, or mobile device. All instruments will be uploaded to this application for NU IRB approval. In addition to the self-report measures (listed below), we will also assess the following demographic variables, including age, gender, and race/ethnicity. We will assess the following self-report measures in each assessment:

	Full Name of Measure	Administered at:	In reference to:
1	Demographics (see uploaded	Baseline (T1) only	
	instruments)		
2	Technology Survey	Baseline (T1) only	Technology/Usability
3	System Usability Scale (SUS)	T2	Technology/Usability
4	Perceived Usefulness Scale (PSU)	T2	Technology/Usability
5	Technology Acceptance Model (TAM)	T2	Technology/Usability
6	Recommendations & Skill Use	T2	Technology/Usability
7	Zarit Burden Interview	All timepoints	Psychological
			Adjustment
8	Oberst Caregiving Burden Scale	All timepoints	Psychological
	(OCBS)		Adjustment
9	Positive Aspects of Caregiving Scale	All timepoints	Psychological
			Adjustment
10	Caregiver reaction assessment	All timepoints	Psychological
			Adjustment
11	Caregiving Mastery subscale of the	All timepoints	Psychological
	Caregiving Appraisal Measure		Adjustment
12	Loneliness/social isolation	All timepoints	Psychological
			Adjustment
13	Psychological wellbeing (NIH Toolbox)	All timepoints	Health Behaviors
14	PROMIS measures (anxiety,	All timepoints	Psychological
	depression, perceived stress, life		Adjustment
	satisfaction, self-efficacy, and meaning		
	and purpose)		
15	Cohen's perceived stress scale	All timepoints	Psychological
			Adjustment
16	Differential Emotions Scale	Daily Throughout	Psychological
		Intervention	Adjustment

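### Do the differing summaries in Sections 1.0 and 22.0, and the unstated set of participants for content completed, call for a change to the pilot's analysis plan?

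*Combined protocol and SAP*

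**What the plan says.** Section 1.0 describes the pilot as a single-arm, pre-post study of 30 caregivers. It plans the "number and percentage of participants retained at the post assessment as well as the means and ranges for the proportion of intervention content completed". Content completed is defined for each person as the "number of pages viewed out of the total possible pages across all skills and lessons in the intervention". The same means and ranges apply to acceptability, defined as participants' "ratings of whether they would recommend SAGE LEAF to other AD caregivers".

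Section 22.0 says: "We will calculate the medians and interquartile range (IQR) for primary measures that assessed the (1) usability, (2) usefulness, (3) feasibility, and (4) acceptability". It does not say which measure stands for feasibility, does not separate the user test from the pilot, and does not repeat retention. Its next sentence adds supplementary engagement metrics from platform data, with home practice completed and videos watched as examples.

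Four other places bear on the point:

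- Section 8.0 (online lessons, which the pilot shares with the user test) lists stored platform data, including "number of log-ins, completed home exercises, number of skills completed". The list is open-ended and does not name page views.
- Section 8.0 (Phase 2 measures) collects "Recommendations & Skill Use" at T2 only and times that assessment from baseline: "T2 (approx. 6-8 weeks from baseline".
- Sections 11.0 and 17.0 keep the data of people who withdraw, and Section 17.0 has those data analysed up to withdrawal. Section 17.0 also lets participants skip questions.
- Section 19.0 names acceptability, adherence and retention as the goals of data collection.

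**The concern.** One construct, acceptability, has two different summaries in one document, and neither section says which governs or that both will be given. If content completed is Section 22.0's unnamed feasibility measure, the same holds for it. Section 1.0 fixes the page denominator but not the set of people: all who consented, all given access, or only those who reach T2.

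This looks important because of what the pilot is meant to show. Section 1.0 says of self-guided programmes that "they are beset by high rates of attrition and poor adherence". A median and IQR can hide a minority who stop early. A T2-only base can leave out those who disappear. Someone may also stop the lessons and still answer at T2, and so count as retained. If an author could choose the summary and the base after seeing the data, completion could look better than it was.

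**Working it through.** The documents give no attrition rate, completion rate or rating scale, so there is no plan figure to reproduce. The only input from the documents is the pilot size of 30. All other inputs below are assumptions chosen to show the mechanism.

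**Are the two sets of summaries compatible?**

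| Measure | Section 1.0 | Section 22.0 | Following both |
|---|---|---|---|
| Recommendation rating | mean, range | median, IQR (acceptability) | all four |
| Content completed | mean, range | median, IQR if it is the feasibility measure; otherwise possibly a supplementary metric with no statistic stated | mean and range at least |
| Retention | number, percentage | not repeated | number, percentage |

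Neither section says its summaries are the only ones, so nothing in one forbids the other.

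**Does following both hide a low tail?** Suppose k of 30 stop after module 1 (1/6 of pages) and the rest view everything. The mean is (30 − k + k/6)/30.

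- k = 3: (27 + 0.5)/30 = 91.7%; median 100%, IQR 100-100%.
- k = 6: (24 + 1)/30 = 83.3%; median 100%, IQR 100-100%, range 17-100%.
- k = 7: the lower quartile stays at 100% under R's type 7 rule. Under type 6 it is 1/6 + 0.75 × 5/6 = 79%.
- k = 8: the lower quartile is 1/6 + 0.25 × 5/6 = 37.5% (type 7) or 16.7% (type 6).

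So up to 6 stoppers can be invisible in the median and IQR under both rules. They are not invisible in the mean and range that Section 1.0 already requires. If all 6 also complete T2, retention reads 30/30, but the mean of 83% and minimum of 17% still expose them.

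For ratings on an assumed 1-5 scale, take 24 raters, 19 giving 5 and 5 giving 1. The median is 5 and the IQR 5-5. The mean is (95 + 5)/24 = 4.17 and the range is 1-5, so Section 1.0's summaries again show the split.

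**How much can the set of participants matter?** Suppose the non-stoppers average 90% of pages (spread evenly over 80-100%), k stoppers view 1/6, and no stopper reaches T2.

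- k = 6: all consented (21.6 + 1)/30 = 75.3%; T2-only 90.0%; gap 14.7 points.
- k = 10: all consented (18 + 1.67)/30 = 65.6%; T2-only 90.0%; gap 24.4 points.
- If every stopper completes T2, the gap is 0.
- Medians move less: 87.4% against 90.0% for k = 6, and 84.7% against 90.0% for k = 10.

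The figure of 24 points is not a ceiling. If 12 of 30 never start and the other 18 view 90%, the all-participant mean is 0.6 × 90% = 54%, a gap of 36 points. But retention would then read 18/30 = 60%. Whichever base was used, the all-participant mean cannot be below the reported mean times the retained proportion, because nobody views less than 0%. The planned retention figure therefore gives the reader a bound.

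**The case for a change.** The strongest reply is that compatible is not the same as promised. An author could cite Section 22.0 alone, report only medians and IQRs, and use the T2 base. Settling the wording beforehand would cost a few lines. Page views are not named in the list of stored data, the number of raters is not promised, and the withdrawal text does not reach non-starters or people lost without formally withdrawing.

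Part of this stands. The acceptability mismatch is explicit, the feasibility measure is unnamed, and the base for content completed is not stated. The rest carries less weight:

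- People who stop lessons but complete T2 do not show up only in content completed. Section 22.0's supplementary metrics would also show them, and log-ins and skills completed are stored as well.
- For formal withdrawers, a T2-only base would sit badly with Section 17.0, which has their data analysed.
- Section 1.0's definition of content completed cannot be applied without page views, and the stored-data list is open-ended.
- Retention is already planned in Section 1.0; not repeating it in Section 22.0 of the same document is no defect. A confidence interval follows from the count: 24/30 gives 80%, exact 95% interval 61-92%.
- An all-consented base is not clearly better. Section 4.0 sends pilot participants their access email only after baseline is completed, so that base could score people who never had access as 0%.
- Rater counts, a named quartile rule and a result that treats non-raters as unfavourable are useful extras, but they correct nothing in the plan.

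**Conclusion.** The difference between the sections is real, but it is missing detail and does not call for a change. Read together, they already yield mean, range, median, IQR and retention number and percentage, and these expose the low tail that a median and IQR alone can hide. The pilot has no progression threshold tied to these figures, and no error rate or sample size depends on them. A careful analyst would report both sets of summaries, state the number contributing to each, and say who is in the content-completed base.

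The effect is confined to how descriptive results read. In the assumed scenarios the base moves the mean by 0 to 24 points, or 36 if 12 of 30 never start. The median moves by about 5 points at most in the even-spread scenarios. The conclusion assumes that Section 1.0's summaries are reported and not treated as replaced by Section 22.0. Nothing in the documents says that they are replaced.
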